**Apatinib in the treatment of HER-2 negative advanced breast cancer
with chest wall metastasis: Multicenter Phase II clinical trial**

Protocol ID: 2016YJZ19

ClinicalTrials.gov ID: NCT02878057

Document date: September, 2020

Introduction

Tumor metastasis is responsible for most of cancer deaths. Once diagnosed of breast cancer (BC), 25-50% of patients will eventually have metastasis in subsequent years. The mechanism of metastasis is a complex, multistep biological process, involving a multitude of genes, angiogenesis and biomolecules. Different molecular subtypes tend to have different initial metastatic sites. For instance, BC with HER2-positive to liver, triple-negative to lung and hormonal receptor positive (HR+) to bone were most common. However, despite of subtype, the rate of chest wall and lymph node metastasis is higher in all molecular subgroups. Recently, Song et al found that neutrophil extracellular traps (NETs) are abundant in the liver metastases of patients with breast and colon cancers, and that serum NETs can predict the occurrence of liver metastases in patients with early-stage BC. This indicates that studying organ specificity of tumor metastasis may also allow us to understand tumor behavior and lead to improvement of our therapeutic approach.

Angiogenesis serves an important role in tumor growth, invasion and metastasis in BC, while vascular endothelial growth factor (VEGF) and its receptors, specifically VEGF receptor 2 (VEGFR2), are predominantly responsible for angiogenic signaling. Bevacizumab (BEV) is a monoclonal antibody that binds to VEGF and inhibits the development of tumor vasculature, which has been proven to significantly increase progression free survival (PFS) when added to first line chemotherapy in MBC. VEGF-tyrosine kinases inhibitors (VEGF-TKIs) such as sunitinib and sorafenib have shown potential anti-tumor efficacy in MBC when combined with chemotherapies.

Apatinib is also an oral TKI that selectively inhibits VEGFR-2, inhibiting tumor angiogenesis, and has reported activity in BC. However, as BC with a chest wall metastasis (CWM) has rich vascular distribution, whether apatinib is also effective for BC with a CWM remains unknown. Precision treatment usually refers to treatment based on molecular markers. Therefore, in current clinical trial designs, organ specificity or organs are usually not the main consideration. Nevertheless, in our clinical practice, we found that type of organ metastasis was difference among molecular subtype. Patients with CWM may have more VEGFR expression, and rich neovascularization, which could have a better response to angiogenesis inhibitors. We found that the using of BEV or apatinib can rapidly shrink the mass in the chest wall, especially when the tumor is filled with rich blood vessels. Therefore, we designed this clinical trial, based on the characteristics of organs. To the best of our knowledge, this is the first study to assess the efficacy and safety of apatinib in HER-2 negative advanced breast cancer (ABC) with a CWM based on organ specificity.

Material and Methods

Patients and eligibility criteria

Inclusion criteria included women (≥ 18 years of age) with HER-2 negative ABC with CWM confirmed by histology or cytological examination, underwent first line chemotherapy regimen or cannot tolerate standard first-line treatment, having Eastern Cooperative Oncology Group performance status (ECOG PS) of 0 or 1, having at least one measurable site of disease according to Response Evaluation Criteria in Solid Tumors (RECIST) 1.1 criteria that has not been previously irradiated. All patients had adequate hematologic, coagulation, hepatic, renal, and cardiac function, and had provided written, informed consent.

Patients were excluded for the following additional reasons: radiotherapy within 28 days before enrollment (radiotherapy to relieve metastatic bone pain before enrollment is permitted, but the irradiated medullary bone shall not exceed 30% of the total amount); symptomatic metastatic carcinoma to central nervous system; other carcinomas within 5 years; uncontrolled hypertension with antihypertensive therapy; ischemia of the myocardium (\geq grade 2) or myocardial infarction, arrhythmia (\geq grade 2, QTcF > 470 ms); grade III-IV cardiac insufficiency according to NYHA standard, or left ventricular ejection fraction (LVEF) < 50%; gastrointestinal disorder or other factors (dysphagia, chronic diarrhea or intestinal obstruction) that could interfere with drug absorption.

The study was conducted in accordance with the World Medical Association Declaration of Helsinki, guidelines of the International Conference for Harmonisation/ Good Clinical Practice. This study was approved by the Ethics Committee of Beijing Cancer Hospital. Written informed consent was provided from all patients (2016YJZ19-GZ01). This trial was registered with ClinicalTrials.gov (NCT02878057).

Drug administration

Initially, all patients received apatinib 500 mg/d as the starting dose, and once a day (qd) 4 weeks as one cycle. Apatinib was administered until disease progression, death, consent withdrawal, unacceptable toxicity after 50% dose of reductions. Besides apatinib, patients with HR+ were given endocrine therapy (ET) at the same time. Apatinib was partially provided by the sponsor, Jiangsu HengRui Medicine Co., Ltd.

Apatinib dose will be allowed to reduce to 250 mg/d if patients experience the following conditions: grade 3/4 of hypertension, nausea, vomiting, proteinuria and diarrhea; grade 4 hematologic adverse events (AEs); other grade 3/4 non-hematologic AEs when investigators

considered dose reduction necessary.

Study design and assessments

This was an open-label, single-arm, phase II study conducted at four centers in China. The primary end point was progression free survival (PFS), defined as time from the date of enrollment (first-dosing) to first documented tumor progression or death of any cause, whichever occurred first.

Secondary end points included objective response rate (ORR), overall survival (OS), disease control rate (DCR), safety and tolerability. ORR was defined as the proportion of eligible patients who achieved a confirmed CR or PR by RECIST 1.1 criteria evaluated by the investigators. OS was defined as time from the date of enrollment to the date of death of any cause or the last follow-up visit. DCR was defined as the proportion of patients who achieved CR, PR and SD for at least 8 weeks. Patients eligible were evaluated by CT or MRI scan at baseline and every 2 cycles (8 weeks) thereafter until disease progression. Follow-up was done every 2 months until death or end of study.

AEs were assessed and graded according to the US National Cancer Institute Common Terminology Criteria for AEs (CTCAE), version 4.03. The safety evaluation was continued until 28 days after the last dose or recovery to grade 1 or 0 from any acute toxicities associated with apatinib.

Statistical analysis

All statistical analyses were performed using SPSS version 17.0 (IBM, Chicago, IL). Median PFS (mPFS) were calculated using the Kaplan–Meier method. Safety data were summarized descriptively using data from all patients who received at least 1 dose of study treatment and had at least 1 post-baseline safety evaluation.

PFS and OS for patents who had at least 8 weeks treatment of apatinib were estimated using Kaplan–Meier method (unless progression during 8 weeks). Log-rank tests and Cox regression models were used for univariate and multivariate survival analysis of prognostic factors, and $p < 0.05$ was considered statistically significant.

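### The 8-week treatment rule for Kaplan–Meier PFS and OS leaves out deaths before week 8 without documented progression, although both endpoint definitions count them

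*Combined protocol and SAP*

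**What the plan says.** Study design and assessments makes PFS the primary endpoint. It runs from enrollment, equated with first dosing, to "first documented tumor progression or death of any cause, whichever occurred first". For OS the same section says: "OS was defined as time from the date of enrollment to the date of death of any cause or the last follow-up visit". Neither definition asks for a minimum time on drug.

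Statistical analysis has two sentences on Kaplan–Meier estimation. The first paragraph says "Median PFS (mPFS) were calculated using the Kaplan–Meier method" and names no population. The second paragraph says "PFS and OS for patents who had at least 8 weeks treatment of apatinib were estimated using Kaplan–Meier method (unless progression during 8 weeks"). The log-rank and Cox sentence follows directly and names no other set.

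The only set based on dosing, "all patients who received at least 1 dose of study treatment" with at least one post-baseline safety evaluation, is given for safety data. No all-treated or intention-to-treat set is defined for efficacy.

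Two other statements matter. Drug administration says: "Apatinib was administered until disease progression, death, consent withdrawal, unacceptable toxicity after 50% dose of reductions". Patients were to be "evaluated by CT or MRI scan at baseline and every 2 cycles (8 weeks) thereafter until disease progression", so no scan is scheduled between baseline and week 8.

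**The concern.** Entry to the set depends on something that happens after baseline, while the clock starts at first dose or enrollment. The progression exception keeps early progressors in, which removes part of the problem. Death is not in the exception. A patient who dies at week 5 with no scan showing progression has had a PFS event and an OS event, yet meets neither condition for entry. Because the first scheduled scan is at week 8, a death before then could easily lack documented progression.

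For OS this is immortal time: every included patient who has not progressed by week 8 must have survived to that point. Patients who stop before week 8 for toxicity or consent withdrawal, without progressing by then, are dropped too, although tolerability is a secondary endpoint.

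The trial has a single arm, so the Kaplan–Meier estimates are themselves the time-to-event results and no control group shares the selection.

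**Working it through.** The plan states no target median, sample size or early-event rate, so there is no figure to reproduce. The check has a textual part and an illustration under assumptions.

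**Text.** Who enters the 8-week set, by the reason treatment ends before week 8:

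| Reason | Event under the PFS definition? | Event under the OS definition? | In the set? |
|---|---|---|---|
| Progression within 8 weeks | Yes | Only if the patient dies | Yes (exception) |
| Death without documented progression | Yes | Yes | No |
| Toxicity or withdrawal, no progression by week 8 | Not at that time | Only if the patient dies | No |

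Progression cannot be read to include death. The PFS definition lists the two as separate events, and Drug administration lists them as separate reasons for apatinib to end.

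**Early deaths only.** Let d be the share of treated patients who die before week 8 without documented progression. Beyond week 8, S_all(t) = (1 − d) × S_restricted(t). If the restricted curve is exponential, median_all = median_restricted × [1 + log2(1 − d)]. The restricted medians of 5.0 months (PFS) and 12 months (OS) are assumed.

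| d | 1 + log2(1 − d) | PFS, all treated | PFS overstated by | OS, all treated |
|---|---|---|---|---|
| 2% | 0.9709 | 4.85 | 3.0% | 11.65 |
| 3% | 0.9561 | 4.78 | 4.6% | 11.47 |
| 5% | 0.9260 | 4.63 | 8.0% | 11.11 |

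A simulation of 2,000,000 patients gave PFS medians of 4.853 at 2% and 4.627 at 5%.

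With a Weibull restricted curve of shape k, median_all = 5.0 × [1 + log2(1 − d)]^(1/k):

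- k = 0.8: 4.819 at 2% and 4.542 at 5% (overstated by 3.8% and 10.1%).
- k = 1.3: 4.888 at 2% and 4.713 at 5% (overstated by 2.3% and 6.1%).

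The calculation can also start from an exponential all-treated median m. The restricted median is then m × [1 − log2(1 − d)]. For m = 5 months this is 5.15 at 2% and 5.37 at 5%, which is 2.9% and 7.4% too high.

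**Early stops only.** Let r be the share dropped for toxicity or withdrawal. By construction they are progression-free at week 8 (1.84 months), since those who progress by then are kept. With h = ln 2 / 5 and HR their later PFS hazard relative to the restricted set, for t > 1.84:

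S_all(t) = (1 − r) × exp(−h t) + r × exp[−HR × h × (t − 1.84)]

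At r = 5% the all-treated median is 5.10 for HR 1 (the restricted set understates by 2.0%), 5.01 for HR 1.5 and 4.94 for HR 2 (overstates by 1.2%). The direction changes where the second exponential equals one half at t = 5: HR = 5 / (5 − 1.84) = 1.58.

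**Both together, r = 5%.** The first term becomes (1 − d − r) × exp(−h t). For d = 2% the all-treated median is 4.96 (HR 1) or 4.80 (HR 2). For d = 5% it is 4.74 or 4.59.

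**The case against.** The strongest reply is that the primary result may not use this set. The median PFS sentence carries no restriction, and the 8-week sentence opens a separate paragraph that leads into the prognostic-factor analyses. If the 8-week set already gave the primary median, the first sentence would be redundant. This reading is possible and cannot be excluded. It does not rescue the plan: no population is stated for the primary median, the plan would hold two PFS estimates without saying which is primary, and for OS the 8-week sentence is the only one there is.

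A second reply is that the parenthesis is loose wording for any PFS event, since its evident purpose is to keep early failures in. That may have been the intent, but the text does not say it and elsewhere separates progression from death.

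A third reply is that the effect is probably small. This stands as a limit. Eligibility (ECOG 0 or 1, adequate organ function) points to few early deaths. Shifts of 0.15 months (5.00 − 4.85) and 0.37 months (5.00 − 4.63) are short beside a scan interval of 1.84 months. In one combined case (d = 2%, r = 5%, HR 1) the net PFS difference is under 1% (5.00 / 4.96 = 1.008). The early-death error nevertheless always favours the drug.

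Finally, a patient who withdraws before week 8 with no scan after baseline would be censored for PFS at time zero, which is numerically the same as exclusion. This is correct. For those patients the PFS change is mainly one of reporting. It does not affect early deaths, or early stops with later follow-up.

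**Conclusion.** The concern holds. As written, the only set named for Kaplan–Meier PFS and OS excludes deaths that the plan's own definitions count as events, and this mechanism can only overstate both curves. If 2% to 5% of treated patients die before week 8 without documented progression, the PFS median is overstated by 3.0% to 8.0% under an exponential model, and by 2.3% to 10.1% across Weibull shapes 0.8 to 1.3. A 12-month OS median would correspond to 11.65 to 11.11 months. If there are no such deaths, this bias is zero.

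Dropping early stops biases PFS in a direction that depends on their prognosis and changes sign near a hazard ratio of 1.6. Its effect on OS was not calculated.

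All rates and medians here are assumptions. The plan states no PFS benchmark, so no changed decision can be shown. The textual conclusion is firm. What stays open is whether the headline median PFS was meant to come from this set or from all patients. The point should be settled before the PFS or OS results are relied on.

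**What to change.** Replace the 8-week sentence with wording such as:

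> The primary set for Kaplan–Meier PFS and OS, including median PFS, is every patient given one or more doses of apatinib, timed from first dose. Every death is an event for OS, and for PFS when no progression was documented earlier. Patients who stop apatinib early without progression remain in the analysis. If consent is withdrawn or follow-up ends, they are censored at the last adequate tumour assessment for PFS and at last contact for OS.

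Use the same set for the log-rank and Cox analyses. Report how many patients the 8-week rule would exclude, split into death, toxicity and withdrawal. Any result in patients treated for 8 weeks or longer should be a supportive landmark analysis with time counted from week 8.

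The cost is SAP wording and a re-run. No visits are added: scans already continue until progression, and the plan states "Follow-up was done every 2 months until death or end of study". The documents do not show whether scans were obtained after early discontinuation. Where they were not, the censoring rule applies and those patients add little PFS information. The reported medians may become slightly less favourable.
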